- If the participant's BAC is greater than 0.00% before signing the informed consent, he/she would have to reschedule the screening, which can be a few hours later or another day. If asked to reschedule, the participant will be asked not to drive home and

to make other transportation arrangements. If no one is available to take the participant home, a study staff member may call a taxi or car service. CARD will cover transportation expenses in this circumstance.

After the participant signs the consent form, they will receive a copy of it. Prior to conducting the first neuroimaging procedure at BU CILSE, study staff will also review the imaging procedures with the participant.

The consent form also specifies that data from the present study (#4299) will be combined with data from the supplemental study (#4890E) if participants sign consent for both studies.

For all other study sessions, participants with BAC levels greater than 0.02% will be asked to remain at the center until their levels reach below 0.02, or reschedule if necessary. Again, if a participant is drunk and is asked to reschedule the appointment, the participant will be asked not to drive home and to make other transportation arrangements. If no one is available to take the participant home, a study staff member may call a taxi or car service.

The first study session will be scheduled within 4-weeks after their in-clinic screening. If the one-month window expires before the participant can come in to CARD again, then the in-clinic screening session will have to be repeated to assess the participant's eligibility for the study.

Participants who meet eligibility for the study following the telephone and in-clinic screening will be notified of their eligibility to participate in our study via telephone by our study staff. Potential participants will be told that they can take up to two weeks to notify us of whether they would like to participate in this study or whether they need more time to decide. Potential participants who need more time to decide, will be told that they can contact us again whenever they're ready, as long as the study hasn't ended. However, as noted above, if there has been more than one-month between the screening and the participant's first treatment session, we may have to repeat the screening process to ensure eligibility for enrollment at that point in time.

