**III. Alcohol Use Related Assessments**

- A) **Alcohol Dependence Scale (ADS)** - Alcohol dependence will be assessed using the ADS. This 25-item scale has an internal consistency reliability estimate of 0.92 (Skinner & Allen 1982).
- B) **Beck Depression Inventory II (BDI-II)** - BDI II will be used to detect depression in participants. The 21-item assessment encompasses all DSM-based depressive symptoms.

The BDI-II has been found to be reliable among medical samples (and it has demonstrated stability among psychiatric ( $r = 0.92$ ) and student ( $r = 0.93$ ) samples (Beck et al., 1996).

- C) **Alcohol Timeline Follow-Back (TLFB)** - TLFB will be used to estimate participants' daily drinking. In this assessment, participants are presented with a calendar and asked to provide retrospective estimates of their daily alcohol consumption over a specified time period. It takes approximately 25-30 minutes to gather 12 months of data, and approximately 10 minutes to gather 90 days of data. The TLFB has a high test-retest reliability and correlates with other established measures of alcohol use (Sobell & Sobell, 1992).
- D) **Clinical Institute Withdrawal Assessment for Alcohol Scale, Revised (CIWA-A)** - CIWA-A will be used to evaluate the severity of withdrawal symptoms. This 10-item scale, shortened from the 15-item CIWA-A scale, retains significant accuracy when compared to the original CIWA-A ( $r=0.99$ ; Sullivan, Sykora, Schneiderman, Naranjo & Sellers, 1989).
- E) **Obsessive Compulsive Drinking Scale (OCDS)** - OCDS will be used to assess alcohol craving and the urge to drink. The OCDS is a 14-item self-report questionnaire developed based on the Yale-Brown Obsessive Compulsive Scale, an interview-based rating scale. It takes approximately 5-10 minutes to complete. The OCDS is significantly correlated with independent measures of alcohol craving and with the amount of alcohol consumed, and has a positive relationship with independent measures of the severity of alcoholism (Anton, Moak, & Latham, 1995).
- F) **Alcohol Use Questionnaire (AUQ)** - AUQ will be used to assess alcohol craving and the urge to drink. The AUQ is an 8-item self-report questionnaire, in which participants rate their agreement or disagreement to statements on a Likert-type scale. AUQ scores are strongly correlated to the severity of alcohol dependence and to cognitive preoccupation with alcohol, and decline with prolonged abstinence from alcohol (Bohn, Krahn, Staehler, 1995)

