### Study Sessions

All participants will be required to have a BAC of 0.02% or less to complete study sessions. Following screening, subjects will receive either ZON or drug placebo (and TC) for 12 weeks, followed by a 2 week taper off medication. Most weekly study sessions will be approximately 45-60 minutes in duration. Session 1 will be approximately 3 hours, while session 12 will be approximately 2 hours in duration. Follow-up data will be collected at the end of the drug taper (week 14) and then again two weeks later (at study week 16). We will allow up to four weeks for completion of this week 16 follow-up phone assessment. Therefore, participants will have a 20-

week window to complete all study procedures before their participation is considered complete. Assessments that will be obtained during the course of the study are shown in Table 1.

We will ask participants to schedule a standing appointment for each week of the 14-week study, with each appointment scheduled 7 days apart. However, we will allow participants to reschedule an appointment between 7-10 days after their previous session if necessary. The length of time until the subsequent session would then be modified in an attempt to re-establish the original schedule. If a session is scheduled beyond this 7-10 day window (i.e., days 11-14), the session will still be conducted but will be considered the next session. The prior session will be considered “missed.” Participants who miss two consecutive sessions during any 14-day period will be tapered off the study medication and withdrawn from the trial for safety reasons. Participants who are withdrawn will be asked to return weekly to complete the medication taper.

*Interventions:*

Medication treatment (Zonisamide vs. placebo) and Take Control will be administered using a double-blind procedure to subjects during scheduled visits over a period of 14 weeks.

I. Zonisamide (ZON):

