All medication records and dispensing will be managed by the nurse administrator. Pills will match the placebo. Based on previous findings (Knapp et al., 2015), ZON dose of 400 mg daily will be used as the target maintenance dose in this study. A final target maintenance ZON dose of 400 mg will be given after a seven week long titration period. Based on the known half-life of ZON, it is expected that it will take approximately 2 weeks to reach steady state for a given dose of ZON. Participants will begin the medication taper schedule at week 12. According to this schedule, participants will be reduced to a dosage of 300 mg for the entirety of week 12, reduced to a dosage of 200 mg for the first three days of week 13, reduced to a dosage of 100 mg for the next three days, and then the participant will be done taking the medication. Therefore, the participant will be completely off of the medication by the day before the week 14 session. Pill placebo will be administered according to the Zonisamide schedule.

Dosage escalation and maintenance regimen

Week 1 + 2	Week 3 + 4	Week 5 + 6	Week 7 – 12 Maintenance
100 mg/day (once a day)	200 mg/day (once a day)	300 mg/day (once a day)	400 mg/day (once a day or two divided doses)

Dosing will be modified, if needed, to adjust for subject tolerance of drug dosing or to reduce adverse drug effects. Verification of medication adherence compliance will entail comparing the patient’s self-report against the number of pills remaining in the medication vial. Pill counts will be conducted at each visit to encourage medication adherence.

Medication will be dispensed according to a two-week dosing schedule by medical personnel at weekly study sessions. Participants will be supplied with two medication bottles at each study visit, containing between 4-7 days of medication in one bottle and 7 days of medication in the other. At any given time, participants may have between 10-17 days of medication in two or three medication bottles. Patients will self-administer medications daily, as directed.

Patients who have to discontinue medication will be permitted to remain in the study and participate in study assessments and will be allowed to continue to receive TC.

Participants who are withdrawn from the study will be tapered off the medication. Any unused medication can be returned during the taper period, either in person or by a postage-paid return envelope we will supply them with.

II. Take Control:

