CONN creates subject-specific ROI files and registers them to the subject space. 99 ROIs will be used as the seeds of interest for whole-brain subject-specific ROI-ROI connectivity analyses.

**Power Analysis:** Power analysis for drinks consumed per day during the last three weeks of treatment were determined using data for the placebo and zonisamide groups from our previous study (Knapp et al., 2015). A power value of 0.9 was found for a group size of 40, with alpha=0.05, and with an effect size of 0.74. In our previous study of ZON approximately 20% of subjects dropped out before week 12 of the study. Consequently, we will randomize 50 subjects per group to reach a target of 40 subjects in week 12 of the present study. Based on data reported by Rubio et al. (2009) for errors of commission on the CPT, a measure of impulsivity, a power value of 0.97 would be obtained for an alpha value of 0.05 for a group size of 40. Based on the findings of Myrick et al., (2008) for the difference between the activation of the ventral striatum for placebo and naltrexone groups a power of 0.88 was seen for an effect size of 0.7 for a group size of 40.

**Safety Analysis:** For safety, subjects will be assessed as having had any serious adverse event during the treatment period or not, and additional analyses will be done by separate types of adverse events. Tolerability will be assessed as a subject being able to continue on the study drug for the entire study duration without requiring discontinuation. The safety and tolerability of the study medications will be first assessed using contingency tables and chi-square tests. Fisher's exact test will be employed for rare adverse events. The chi-square analysis will be followed by logistic regression analyses, adjusting for the stratification factor. Time to drug discontinuation for serious adverse events and time to withdrawal from the study for any reason will be assessed using Kaplan-Meier survival curves and compared between study treatments using the log rank test. Poisson regression will be used to evaluate the rate of serious adverse events by arm stratified by the time periods of dosage escalation, dosage maintenance, and dosage taper.

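### Missing two consecutive sessions ends trial participation as well as study drug, with no drinking follow-up planned afterwards, which could bias the drinking comparison

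*Combined protocol and SAP*

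**What the plan says.** Four parts of the combined protocol and SAP bear on this point.

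- **Missed visits (Section L, Study Sessions).** Participants who miss two consecutive sessions in a 14-day period "will be tapered off the study medication and withdrawn from the trial for safety reasons". The next sentence gives the only contact planned for them: "Participants who are withdrawn will be asked to return weekly to complete the medication taper".
- **Stopping drug (same section, Zonisamide).** "Patients who have to discontinue medication will be permitted to remain in the study and participate in study assessments".
- **Alcohol limit at sessions.** Study Sessions states: "All participants will be required to have a BAC of 0.02% or less to complete study sessions". Section K adds that at sessions after consent "participants with BAC levels greater than 0.02% will be asked to remain at the center until their levels reach below 0.02, or reschedule if necessary".
- **Analysis and sample size.** Data Analysis, item 4, compares drinking over the 12 treatment weeks with a repeated-measures mixed model and baseline drinking as a covariate. It names no analysis set, no missing-data assumption and no sensitivity analysis. Power Analysis reports that in the team's previous zonisamide study "approximately 20% of subjects dropped out before week 12 of the study", and so randomises 50 per arm to have 40 at week 12.

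The TLFB itself is a retrospective calendar interview. The description under Alcohol Use Related Assessments says it takes "approximately 10 minutes to gather 90 days of data". A telephone TLFB is already planned at week 16 (Post-Treatment Period), and Covid-19 Protocols says that all study sessions are now held by video.

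**The concern.** The plan already treats stopping drug and stopping assessment as separate decisions, but it does not do so for people stopped because of missed visits. The stated reason for the rule is safety. That bears on continued medication, and it does not explain why drinking should no longer be recorded.

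The group affected matters because the plan itself links drinking to attendance. A participant over the alcohol limit cannot complete the session and must wait or rebook, and a visit that slips to days 11 to 14 counts as the next session, with the prior one recorded as missed. Heavy drinking can therefore contribute to two missed sessions, and the drinking in that gap is what goes unrecorded.

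The mixed model gives valid estimates if, given baseline and the drinking already observed, dropout does not depend on the drinking that was not observed. Loss driven by a current relapse could break that condition. If the loss also differs by arm, the estimated effects on drinks per day and percent days drinking would be shifted. Nothing in the analysis plan would show how far.

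**Working it through.** **Inputs from the documents (Power Analysis).** Standardised effect 0.74, alpha 0.05, 40 per arm at week 12, 50 per arm randomised, 20% dropout, stated power 0.9. The endpoint is drinks per day in the last three treatment weeks.

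**Assumed inputs.** The documents give no withdrawal rate by arm, no figure for drinking after withdrawal, and no figure for drug effect remaining after stopping. These are varied below.

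**Step 1: the plan's own figure.** For a two-sided, two-sample t-test the noncentrality is d × √(n/2) = 0.74 × √20 = 3.31 on 78 degrees of freedom. Power is 0.905, which matches the stated 0.9. The inflation is also right: 40 / (1 − 0.20) = 50.

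**Step 2: possible bias.** Let p be the share of an arm whose late drinking is lost, and k the amount, in SD, by which their true drinking exceeds the model's prediction for them. That arm's estimated mean is then too low by p × k. With benefit defined as placebo minus zonisamide and the same k in both arms:

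error in estimated benefit = −k × (p_placebo − p_ZON)

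| Placebo / ZON lost | k = 0.5 | k = 1 | Share of 0.74 | Effect on ZON benefit |
|---|---|---|---|---|
| 20% / 20% | 0 | 0 | 0 | none |
| 25% / 15% | −0.05 SD | −0.10 SD | 7% to 14% | understated |
| 15% / 25% | +0.05 SD | +0.10 SD | 7% to 14% | overstated |
| 30% / 10% | −0.10 SD | −0.20 SD | 14% to 27% | understated |

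For example, 1 × (0.25 − 0.15) = 0.10 SD, and 0.10 / 0.74 = 13.5%.

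Two limits apply. Each row averages 20% lost across the arms, which is the plan's figure for all causes. If this rule causes only part of the gap between arms, its contribution shrinks in proportion. The scale is also that of the last three weeks. An average over all 12 weeks includes observed weeks before withdrawal, so the bias there would be smaller.

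**Step 3: what retention does to power.** Keep outcomes on all 50 per arm, and suppose the 20% who stopped retain a fraction r of the drug effect. The effect becomes 0.74 × (0.8 + 0.2r).

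| r | Effect | Power, 50 per arm |
|---|---|---|
| 1 | 0.740 | 0.956 |
| 0.5 | 0.666 | 0.909 |
| 0 | 0.592 | 0.834 |

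Retention matches 40 completers (0.905) when the effect is about 0.74 × √(40/50) = 0.662. That gives r = (0.662/0.74 − 0.8) / 0.2, or about 0.47. Retention can therefore raise or lower power.

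**The case against.** The strongest reply is that the documents are silent rather than wrong. No sentence says that TLFB stops on withdrawal. Withdrawn participants are asked back weekly for the taper, the assessment table lists TLFB at nearly every contact, and nothing excludes them from the week 16 call. A link with drinking is also not enough to make data missing not at random. The model uses baseline and earlier TLFB, so dropout explained by recorded drinking is handled. Missed visits may reflect side effects or logistics, rescheduling is allowed, and video sessions make attendance easier. Withdrawal by arm is also watched: time to withdrawal is compared by log-rank test, and the DSMB sees retention and dropout reasons by arm.

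Much of this stands, and it rules out several stronger readings that a reader might infer:

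- **That these participants have relapsed.** The alcohol limit makes this plausible, but no passage gives data on it.
- **That the comparison is biased.** This is a risk. Its size and sign depend on unrecorded drinking and on differences between arms, and it vanishes with equal rates and equal shifts.
- **That the rule costs 10 of 50 per arm.** The 20% is dropout from all causes in a previous study, and the share due to missed visits is unknown. Participants may also leave by choice, after referral for detoxification, or for depression or suicidality.
- **That the trial is underpowered.** The 20% loss is already in the sample size.

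The reply does not remove the core point. Withdrawal from the trial ordinarily ends outcome collection, the taper is the only stated purpose of the later visits, and the plan spells out continued assessment for the other group but not for this one. Comparing withdrawal times would reveal a difference between arms, but would not recover the missing drinking data or show how far they could move the result.

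**Conclusion.** The point holds as a design weakness that should be corrected. Applied as written, the rule removes participants from the trial as well as from drug, and provides no drinking follow-up for a group whose attendance the plan itself ties to alcohol level. The lost data could be missing not at random and could bias the item 4 comparison towards or away from zonisamide. On the assumed 25% versus 15% loss and a shift of 0.5 to 1 SD beyond the model's prediction, the bias is 0.05 to 0.10 SD, or 7% to 14% of the planning effect. These inputs are illustrative, and the true figures cannot be derived from the documents.

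The power statement is correct and needs no change. The case for retention is validity: a comparison of the arms as randomised. No view is taken on the missed-visit drug rule or the taper.

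**What to change.** 1. Reconcile Study Sessions with the Zonisamide subsection, so that stopping drug for missed visits does not end outcome follow-up. This change leaves the drug and taper rules as they are.
2. State that TLFB will be sought by phone or video through week 12 and at week 16 from every randomised participant who still consents, with a retrospective interview to cover missed weeks.
3. In Data Analysis, item 4, define the analysis set as all randomised participants, analysed as randomised, and state the missing-data assumption of the mixed model.
4. Add a missing-not-at-random sensitivity analysis, for example one that shifts the unobserved drinking by a range of SD values separately in each arm and reports where the conclusion changes.

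The cost is a short amendment and a few brief calls. At the plan's 20% loss, and if every loss came through this rule, that would be at most about 20 people (2 × 10). Some will not respond, recall over missed weeks will be less precise, and the estimated effect may be diluted by time off drug, with the power range shown above.

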#### Digital Recordings

Recordings of the clinical interview portion of the in-clinic screening session will be digitally recorded to ensure adherence to the screening protocol and inter-rater reliability for the administration of the clinical assessments. In addition, digital recordings will be collected during the assessments occurring throughout treatment. In particular, the neuropsychological evaluation portion will be recorded to determine adherence and reliability of the study procedures.

The digital recordings will be stored using a highly secure, password protected drive. We will label these files with a code. The digital recordings will be destroyed along with the other study data, after 7 years following the end of the study.

#### Data Analysis

1. Demonstrate that ZON will attenuate changes resulting from performance on alcohol-word and negative-word Stroop tasks in the activity of frontal-parietal and midbrain regions and the connectivity to networks associated with these regions in AUD subjects. Our working hypothesis is that midbrain activity will be lower in ZON treated subjects than in placebo subjects following performance on alcohol and negative emotion Stroop task, which will occur in association with enhanced mid-brain-frontal connectivity and increased synchrony.

Fixed effects models will be used to analyze data for brain activation in regions of interest, with treatment group as a between group factor and Stroop task type and order of stimuli presentation will be within subject factors. Regions of interest will include parahippocampal gyri, midbrain substantia nigra and red nucleus, dorso-lateral prefrontal cortex, and cerebellum.

Connectivity will be assessed using the Free Surfer analysis described below. Seeds will be used for the dorsolateral prefrontal cortex and the midbrain (substantia nigra) following Muller-Oehring et al. (2013).

2. Demonstrate that ZON administration attenuates the enhanced regional brain activity and craving- induced by exposure to alcohol related cues in AUD subjects. Our hypothesis is that exposure to alcohol-related cues will increase brain activity in select limbic and prefrontal areas to a lesser degree in ZON as compared to placebo treated AUD subjects.

Fixed effects models will be used to analyze data for brain activation in regions of interest, with treatment group as a between group factor and stimulus type and order of stimuli presentation was within subject factors. Regions of interest, based on the meta-analysis of Schacht et al. (2013), will include the ventral striatum, medial prefrontal cortex, and the anterior cingulate cortex.

3. Demonstrate that the ZON induced changes in brain activity are predictive of reduced ethanol consumption.

Logistic regression analysis will be used to evaluate zonisamide-induced decreases in the BOLD response in the ventral striatum and the medial prefrontal cortex as predictors of complete abstinence or reduction to safe drinking levels (defined as consumption of no more than more than 2 standard drinks per day) during study weeks 10 to 12.

4. Replicate the finding that ZON will reduce alcohol consumption in AUD subjects. Our working hypothesis is that the drinks consumed per day and percent days drinking will be significantly lower in AUD subjects receiving ZON than in those treated with placebo.

Drinking measures derived from the TLFB data will include the percent days drinking, the number of drinks consumed per day, and the percent days heavy drinking. Heavy drinking will be defined as 4 or more drinks per day for women and 5 or more drinks per day for men.

Alcohol consumption measures will be analyzed using repeated measures mixed models analysis using SAS PROC MIXED (ver 9.3, SAS Institute, Cary, NC) with baseline values for these measures used as covariates. Comparisons will be made for data obtained for the 12 week treatment period for the two conditions.

5. Demonstrate that ZON administration will reduce impulsive and risk taking behaviors. Our working hypothesis is that the ZON will decrease risk taking behavior as assessed using the Rogers Risk Task and the Balloon Analog Risk Task and impulsivity as measured using the Go/NoGo and the Continuous Performance Test (CPT).

Repeated measures mixed models analysis will be used to analyze data obtained for pre-randomization and week 12 data for the Rogers Risk Task, the Balloon Analog Risk Task, the Go/NoGoTask, the CPT, and Go/No Go. Model generated group least square means values for week 12 will be compared using student t-tests.

[name] will provide statistical consultation. He will not have access to identifiable information and will not have any contact with study participants.

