#### **Analysis**

The images will be analyzed using FSL 4.1.1 with the FMRI Expert Analysis Tool (FEAT) v5.98 (Smith et al., 2004; Jenkinson et al., 2012). FSL's general linear model will be used to

model each subject's BOLD response to each explanatory variable (EV). The fMRI data will be co-registered to MNI space and regions of significant activation will be determined through using the Harvard-Oxford Structural Atlas included with FSL (Makris et al., 2006; Frazier et al., 2005; Desikan et al., 2006; Goldstein et al., 2007). In second and third level analyses, we will use cluster thresholding with a Z threshold of 2.3 and a cluster p threshold of 0.05. We will use a fixed effects model for these analyses. All analyses of the fMRI data will include active task > control condition contrasts as well as control > active task contrasts as a reality check.

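### Aims 2 and 5 each set out to demonstrate an effect over several regions or tasks, but name no deciding measure and no adjustment; power is stated for only one measure in each, and Aim 1 also lacks a deciding measure.

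*Combined protocol and SAP*

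**What the plan says.** In Section L, Data Analysis, Aims 1, 2 and 5 are each introduced as something the trial will demonstrate.

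- **Aim 1 (Stroop).** "Regions of interest will include parahippocampal gyri, midbrain substantia nigra and red nucleus, dorso-lateral prefrontal cortex, and cerebellum". The working hypothesis is directional: "Our working hypothesis is that midbrain activity will be lower in ZON treated subjects than in placebo subjects". It adds enhanced midbrain-frontal connectivity and synchrony. The Study Summary (Section G) states the Stroop hypothesis as connectivity only.
- **Aim 2 (alcohol cues).** The regions "will include the ventral striatum, medial prefrontal cortex, and the anterior cingulate cortex".
- **Aim 5 (risk taking and impulsivity).** The measures are "the Rogers Risk Task, the Balloon Analog Risk Task, the Go/NoGoTask, the CPT, and Go/No Go". Go/No-Go appears twice, so there are four distinct tasks. "Model generated group least square means values for week 12 will be compared using student t-tests".

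No region or task is named as primary, no adjustment across them is described, and nothing says how many must be positive for an aim to be met. The DSMB data-quality text in Section R mentions primary and secondary outcomes in general terms but does not list them.

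The imaging Analysis section sets "cluster thresholding with a Z threshold of 2.3 and a cluster p threshold of 0.05". The Power Analysis says of the ventral striatum that "a power of 0.88 was seen for an effect size of 0.7 for a group size of 40", and of CPT commission errors that "a power value of 0.97 would be obtained for an alpha value of 0.05 for a group size of 40". It gives no power for Aim 1.

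**The concern.** When an aim is worded as a demonstration and rests on several measures with no rule, it can be claimed on whichever measure crosses the threshold. The false-positive rate for the aim then exceeds that of a single test. If an adjustment is added later, the stated powers no longer describe the aim, because each was worked out for one measure taking the full significance level. A reader of the results could not tell whether the ventral striatum, say, was the intended test of Aim 2 or the region that happened to be positive.

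**Working it through.** **Inputs.** From the Power Analysis: 40 per group at week 12; d = 0.7 and power 0.88 for the ventral striatum; power 0.97 at alpha 0.05 for CPT commission errors, with no effect size. From Data Analysis: three regions (Aim 2) and four distinct tasks (Aim 5). Assumed: each measure is tested at two-sided 0.05. Data Analysis gives no level; this one is inferred from the Power Analysis and the cluster threshold.

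**1. The plan's own figures.** For a two-sample t-test, the noncentrality is d × √(n/2), with 78 degrees of freedom.
- Ventral striatum: 0.7 × √20 = 3.130. Two-sided 0.05 (critical t 1.991) gives power 0.871; the normal approximation gives 0.879. The stated 0.88 is reproduced. One-sided 0.05 would give about 0.93, which does not match.
- CPT: the power cannot be reproduced forward without an effect size. Solving back from 0.97 at two-sided 0.05 gives d = 0.87 (t) or 0.86 (normal).

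**2. At least one false positive, either direction.** For k independent tests this is 1 − 0.95^k.
- Aim 2, k = 3: 1 − 0.95³ = 14.3%.
- Aim 5, k = 4: 1 − 0.95⁴ = 18.5%.
- With an assumed correlation of 0.5 between all pairs: about 12.5% and 15.6%.

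**3. At least one false positive in the favourable direction.** The aims are directional, so a false claim needs the favourable tail, 0.025 per test.
- Aim 2: 1 − 0.975³ = 7.3%; at correlation 0.5, about 6.3%.
- Aim 5: 1 − 0.975⁴ = 9.6%; at correlation 0.5, about 7.8%.
- A single test: 2.5%.

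**4. Power under Bonferroni, 40 per group.**

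| Measure | Level | Power (t) | Power (normal) |
|---|---|---|---|
| Ventral striatum, d = 0.7 | 0.05 | 0.871 | 0.879 |
| Ventral striatum, d = 0.7 | 0.05/3 = 0.0167 | 0.751 | 0.769 |
| CPT, back-solved d | 0.05 | 0.97 | 0.97 |
| CPT, back-solved d | 0.05/2 = 0.025 | 0.943 | 0.945 |
| CPT, back-solved d | 0.05/4 = 0.0125 | 0.905 | 0.910 |

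**5. Cost of recovering the power by sample size instead.** By the normal approximation, n = 2(z for the level + z for the power)²/d².
- Aim 2: 2 × (2.394 + 1.175)²/0.7² ≈ 52 per group.
- Aim 5: 2 × (2.498 + 1.881)²/0.859² ≈ 52 per group.
- At the plan's 20% dropout, 52/0.8 = 65 randomized per group, against the planned 50.

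**The case against.** The strongest reply concerns imaging. If the cluster threshold is applied to one whole-brain map per contrast, with significant areas then located by atlas, its nominal 5% already covers every region in that map, and the Aim 2 rates above do not apply within that contrast. This stands as a limit. Data Analysis, however, describes models of activation in regions of interest, which can equally be read as one model per region, and the plan does not say which is meant. The cluster threshold has no bearing on the Aim 5 tasks.

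Three stronger readings are tempting, and the documents do not support them.

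- *The 0.88 and 0.97 are wrong, or hold only if one region and one task carry their aims.* Unadjusted, each is a valid power for its own measure however many others are tested. They fail only as aim-level powers with error held at 5%, a requirement the plan does not state.
- *Every measure is read at 0.05, so the aims carry error rates of 14% to 23%.* The per-test level is inferred. The 23% for Aim 1 (1 − 0.95⁵ = 22.6%) counts substantia nigra and red nucleus separately; four items give 18.5%. All these rates count both directions, and the favourable-direction rates are about half as large. The reservation about whole-brain maps applies to Aim 1 as well.
- *Substantia nigra activity should decide Aim 1, and the CPT alone Aim 5.* The first conflicts with the connectivity hypothesis in the Study Summary. The second drops the risk-taking half of Aim 5, which would be a scientific change.

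Aim 1's region list also omits any parietal region, although the aim claims frontal-parietal effects, and it includes parahippocampal gyri and cerebellum, which neither the aim nor its hypothesis mentions. That is a separate drafting point, not part of the multiplicity argument.

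**Conclusion.** The concern holds in limited form. Aims 2 and 5 have no deciding measure, adjustment or success rule, and power is stated for one measure in each. The false-positive rates in either direction are about 13-14% (Aim 2) and 16-19% (Aim 5). In the favourable direction they are about 6-7% and 8-10%, against 2.5% for a single test. They rest on two-sided 0.05 per measure and correlation between 0 and 0.5; for Aim 2 they also require separate regional models. Bonferroni would take ventral striatum power to about 0.75, below 0.80, and CPT power to about 0.91, a modest loss that depends on a back-solved effect size. Aim 1 has the same gap in its decision rule, and its lead hypothesis differs between Data Analysis and the Study Summary.

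**What to change.** - **Aim 2.** Name ventral striatum as the deciding region at two-sided 0.05, and state whether it is tested in its own model or within a whole-brain map. Report the other two regions as supportive, with Holm adjustment. Tested in its own model, the deciding region keeps the stated 0.88 as a single-test power.
- **Aim 5.** Either apply Holm across the four tasks with one pre-named score each, or name one measure per construct (CPT commission errors for impulsivity, and the Rogers or the Balloon task for risk taking) with Holm across the two. Describe 0.97 as single-test power, about 0.91 at 0.05/4 (about 0.94 at 0.05/2). Define the commission-error score: the CPT description under Neuropsychological Assessments gives two scores, and neither is a commission-error count.
- **Aim 1.** Have the investigators name one deciding measure before unblinding, reconciling midbrain activity in Data Analysis with midbrain-frontal connectivity in the Study Summary. Attach no power figure to it, since the plan has none.

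This needs wording only and no extra participants. The cost is that supportive measures can no longer carry an aim alone at an unadjusted 0.05, and that Aim 5 accepts the lower adjusted power.
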